1.0 PROTOCOL SYNOPSIS

Sponsor: Xalud Therapeutics, Inc./Xalud Therapeutics Australia Pty LTD

Study Number: Protocol XT-150-2-0204

Product Name: XT-150

Protocol Title: A Double-Blind, Placebo-Controlled Assessment of the Tolerability and Efficacy of

XT-150 for the Treatment of Moderate to Severe Pain Due to Osteoarthritis of the Knee

Planned Study Centers: 5 (US and Australia)

Phase of Development: 2

Objectives

Primary: To confirm the safety and tolerability of intra-articularly-injected XT-150

Secondary: To establish analgesic efficacy of intra-articularly-injected XT-150

Study Design

This is a Phase 2 safety and efficacy study of XT-150 in adult participants experiencing moderate to severe pain due to osteoarthritis of the knee.

Participants will provide informed consent and meet all study eligibility criteria before any study procedures are initiated. Baseline confirmation of study eligibility will be completed the day before or day of study drug administration. The Index Knee for study drug injection will be the OA-affected joint identified by Kellgren-Lawrence grade of 2 or 3; and WOMAC Pain Subscale \geq 8 on a scale of 20.

Study drug will be administered by intra-articular (IA) injection into the joint space of the Index Knee.

About 270 participants will be randomly enrolled into 1 of 3 treatment groups (approximately 90 participants/ group). Treatment Groups:

- A. Placebo (1 mL)
- B. 150 μg XT-150 (1 mL)
- C. 450 µg XT-150 (1 mL)

Participants will undergo the study in 2 stages, A and B:

- D. Placebo-controlled for 6 months
- E. Continued follow up for 6 months with the option of randomly receiving a single 150 μg or 450 μg injection as the second injection to the Index Knee (knee dosed in Stage A).

Safety parameters and efficacy endpoints for each participant will be evaluated monthly for about 1 year from the first XT-150 dose (Stage A, Day 0)

The Schedule of Assessments and Procedures is presented in Table 1 (Stage A) and Table 2 (Stage B). Day 0 is defined as the day of study drug administration. Subsequent study days are defined by the number of consecutive calendar days after drug administration.

Number of Participants and Treatment Groups:

About 270 participants will be enrolled in one of 3 treatment groups (90 participants/group) and evaluated.

Inclusion Criteria

Participants are required to meet ALL of the following inclusion criteria:

- 1. Symptomatic disease due to osteoarthritis, defined as a WOMAC Pain score ≥ 8 (worst possible = 20)
- 2. Focused Analgesia Selection Test (Analgesic Solutions, Wayland, MA) will be used to determine whether patients can report pain with sufficient consistency to enter the clinical trial (See Appendix 4)
- 3. Males and females between 45 and 85 years of age, inclusive
- 4. Kellgren-Lawrence grading of 2 or 3 within the last 6 months
- 5. Stable analgesic regimen during the 4 weeks prior to enrollment
- 6. In the judgment of the Investigator, acceptable general medical condition
- 7. Life expectancy >6 months
- 8. Male and female participants who are heterosexually active and not surgically sterile must agree to use effective contraception, including abstinence, for the duration of the study
- 9. Have suitable knee joint anatomy for intra-articular injection
- 10. Willing and able to return for the follow-up (FU) visits
- 11. Able to read and understand study instructions, and willing and able to comply with all study procedures

Exclusion Criteria

Participants must NOT meet any of the following exclusion criteria:

- 1. Hypersensitivity, allergy, or significant reaction to any ingredient of the study drug, including double-stranded DNA,
- 2. Previously received XT-150 injection(s)
- 3. Scheduled partial or complete knee replacement within 6 months; participant agrees not to schedule a knee replacement during Stage A of the study
- 4. History of knee arthroplasty on the Index Knee, i.e., selected for study injection(s)
- 5. History of rheumatoid arthritis or other inflammatory disease
- 6. History of immunosuppressive therapy; systemic steroids in the last 3 months
- 7. Received knee injection with hyaluronic acid or stem-cells in the last 6 months
- 8. Knee injection of glucocorticoid in the last 3 months
- 9. Current treatment with systemic immunosuppressive (systemic corticosteroid therapy or other strong immunosuppressant)
- 10. Currently receiving systemic chemotherapy or radiation therapy for malignancy
- 11. Clinically significant hepatic disease as indicated by clinical laboratory results ≥3 times the upper limit of normal for any liver function test (e.g., aspartate aminotransferase, alanine aminotransferase)
- 12. Severe anemia (Grade 3; hemoglobin <8.0 g/dL, <4.9 mmol/L, <80 g/L; transfusion indicated), Grade 1 white cell counts (lymphocytes <LLN $800/\text{mm}^3$; <LLN 0.8×10^9 /L, neutrophils <LLN $1500/\text{mm}^3$; <LLN 1.5×10^9 /L)
- 13. Positive serology for human immunodeficiency virus, hepatitis B virus, or hepatitis C virus

- 14. Significant neuropsychiatric conditions; dementia, major depression, or altered mental state that in the opinion of the Investigator will interfere with study participation
- 15. Current treatment with systemic antibiotics or antivirals (EXCEPTION: topical treatments)
- 16. Current anticoagulant or anti-platelet treatment (e.g., warfarin, heparins, factor X inhibitors, clopidogrel, prasugrel, ticagrelor, or dipyridamole). Low-dose (≤ 325 mg/day) aspirin is permitted.
- 17. Known or suspected history of active alcohol or intravenous/oral drug abuse within 1 year before the screening visit
- 18. Use of any investigational drug or device within 3 months before enrollment or current participation in a trial that included intervention with a drug or device; or currently participating in an investigational drug or device study
- 19. Any condition that, in the opinion of the Investigator, could compromise the safety of the participant, the participant's ability to communicate with the study staff, or the quality of the data

Test Product, Dose, and Mode of Administration

XT-150 is a plasmid DNA (buffered saline solution,) formulated in phosphate-

Participants will be randomly enrolled into 1 of 3 treatment arms to receive either Placebo or XT-150 (150 μ g or 450 μ g) as a single, 1-mL, intra-articular knee injection.

Comparator

Phosphate-buffered saline for injection (placebo) will be the comparator for this study.

Duration of Treatment

Participation will require a commitment of approximately 1 year of safety, tolerability, and efficacy evaluation. Additionally, a screening visit will occur up to 30 days before enrollment.

Baseline assessments to confirm study eligibility will be completed no more than 1 day before study drug administration. Day 0 is defined as the day of study drug administration. Subsequent study days are defined by the number of consecutive calendar days after drug administration.

Follow-up visits will occur on Study Days 7, 30, and about monthly thereafter for 1 year.

If a participant fails to participate in the follow-up visits, multiple efforts will be made to determine the reason(s), including contacts by telephone and/or registered letter requesting that the participant contact the site and complete the termination assessments.

Criteria for Outcome Measures

Safety

Safety assessments will be recorded throughout the study. All participants will be assessed with the measures below from signing of the informed consent form (ICF) throughout the study.

- Adverse events and concomitant medications used
- Vital signs (temperature and the collection site [i.e. oral, rectal, temporal, or tympanic], heart rate, blood pressure, and respiratory rate)
- Physical examination including all major organ systems
- Injection site examination

Xalud Therapeutics, Inc. Protocol XT-150-2-0204

Safety assessments conducted after completion of the study by all participants include serum assay results for anti-IL-10 antibody.

Efficacy

[figure not shown]
Efficacy assessments will be recorded throughout the study as described in Table 1 and Table 2.

The primary efficacy outcome measure is whether the subject achieves at least a 30% improvement from baseline in WOMAC Pain Score (obtained from the KOOS questionnaire) at Day 180, as recorded on a 0 to 20 point scale with 20 being the maximum (worst) score.

Key secondary efficacy outcome measures are:

- Change from baseline in the WOMAC Function Score (from KOOS questionnaire) at Day 180
- Change from baseline in patient response at Day 180, using a scale of 1 5, to the OA question: "Considering all the ways the OA in your knee affects you, how are you doing today?", with 1 being very good (asymptomatic and no limitation of normal activities) to 5, very poor (very severe, intolerable symptoms and inability to carry out normal activities)

Additional endpoints include:

Statistical Methods

Efficacy measures will be recorded at baseline (before XT-150 injection) and at each study visit, starting at Day 7 [± 1 day].

All participants will be included in the safety analysis. The incidence of treatment-emergent AEs will be presented by treatment group and system organ class and preferred term according to the Medical Dictionary of Regulatory Affairs (MedDRA®) version 18 or higher, relationship to the study drug, and severity. Adverse events will be graded using the CTCAE v5.0. Descriptive statistics and the change from baseline of vital signs, and laboratory assessments will be presented, as will a summary of abnormal physical examination findings. Adverse events leading to discontinuation will be reported to the respective ethics committees or Institutional Review Boards (IRBs).

Table 1. Schedule of Assessments and Procedures - Stage A

	Screen	Baseline ^a	Follow up Visit Day ^l						
Scheduled Event	Day -30 to Baseline	Day 0	7 (±1)	30 (±2)	60 (±7)	90 (±7)	120 (±7)	150 (±7)	180 (± 7)
Informed consent b	X								
Complete medical history and physical examination ^c	X								
Kellgren-Lawrence grading (may require new radiograph)	X								
Quantitative Sensory Testing	X								
Patient training on pain reporting	X	X	X	X	X	X	X	X	X
Record prior medications d	X								
Efficacy Assessments									
KOOS/WOMAC e	X	X	X	X	X	X	X	X	X
BPI		X	X	X	X	X	X	X	X
Patient response to OA questionf		X	X	X	X	X	X	X	X
		X	X	X	X	X	X	X	X
		X		X	X		X		X
		X	X	X	X	X	X	X	X
Clinical Assessments									
Brief physical examination		X	X	X	X	X	X	X	X
Record height and weight, calculate BMI	X								X
Vital signs	X	X	X	X	X	X	X	X	X
Clinical exam of the treated joints	X	X	X	X	X	X	X	X	X
Record AEs		X	X	X	X	X	X	X	X
Record SAEs		X	X	X	X	X	X	X	X
Record concomitant medications		X	X	X	X	X	X	X	X
Laboratory Assessments									
HIV, Hepatitis B and C	X								
Serum pregnancy ⁱ	X								
PT/INR, PTT	X				X				
CBC with differential and platelets count	X				X				

Sahadulad France	Screen	Baselinea	Follow up Visit Day ^l						
Scheduled Event	Day -30 to Baseline	Day 0	7 (±1)	30 (±2)	60 (±7)	90 (±7)	120 (±7)	150 (±7)	180 (± 7)
Serum chemistry	X				X				
Serum for anti-IL-10 antibody assessments		X	X	X	X				X
Study Drug Administration									
Enroll participant ^j		X							
Administer study drug ^k		X							X

AE = adverse event; BMI = body mass index; BPI = Brief Pain Inventory of Intensity and Interference; CBC = complete blood count; INR = international normalized ratio; ; IL-10 = interleukin 10; KOOS=Knee injury and Osteoarthritis Outcome Score (includes WOMAC measures); PT = prothrombin time; PTT = partial thromboplast in time; SAE = serious adverse event

[figure not shown]
Footnotes to Table 1

- a. Baseline assessments are performed within 1 day before drug injection.
- b. Informed consent must be obtained before initiating any study procedures.
- c. Obtain complete, relevant, medical, and surgical history (including currently active conditions and inactive pain conditions diagnosed) at the Screening visit. Update medical and surgical and pain treatment history at the baseline visit. The physical examination includes the injection site for infections or reactions.
- d. Record prior medications, including prescription and nonprescription medications and herbal supplements. Update prior medications at the baseline visit.
- e. WOMAC Total Score at Screening > 8
- f. Participant assessment will be recorded in response to the question: "Considering all the ways the OA in your knee affects you, how are you doing today?" on a scale of 1 to 5, 5 being worst
- i. Women of child-bearing potential
- Verify that the participant meets all study inclusion and exclusion criteria before enrollment as close to study drug dosing as
 possible.
- k. Participant will receive a single, 1-mL dose of study drug into the intra-articular space of the knee on Day 0. Participant may elect a second injection on Day 180 (enters Stage B) after efficacy assessments have been recorded.
- A telephone call documenting safety and efficacy assessments may be used for participants unable to physically attend follow
 up visits due to COVID-19 infection or corona virus exposure concerns

Table 2. Schedule of Assessments and Procedures - Stage B

Scheduled Event	Follow up Visit Day ^d							
	210	240	270	300	330	360		
	(±7)	(±7)	(±7)	(±7)	(±7)	(±7)		
KOOS/WOMAC	X	X	X	X	X	X		
BPI	X	X	X	X	X	X		
Patient response to OA question	X	X	X	X	X	X		
	X	X	X	X	X	X		
						X		
Brief physical examination	X	X	X	X	X	X		
Record height and weight, calculate BMI						X		
Vital signs	X	X	X	X	X	X		
Clinical exam of the treated joints	X	X	X	X	X	X		
Record AEs	X	X	X	X	X	X		
Record SAEs	X	X	X	X	X	X		
	X	X	X	X	X	X		
Record concomitant medications	X	X	X	X	X	X		
Serum for anti-IL-10 antibody assessments						X		
Serum pregnancy test ^b						X		
Administer study drug ^c	X	X	X	X	X			

Footnotes to Table 2

- b. Women of child-bearing potential
 c. Participants may elect for one (1) XT-150 IA injection into the Index Knee at any point during Stage B up to Day 330, inclusive. The XT-150 dose (150 μg or 450 μg) will be randomly assigned.
- d. A telephone call documenting safety and efficacy assessments may be used for participants unable to physically attend follow up visits due to COVID19 infection or corona virus exposure concerns

$\mathbf{T}A$	BLE OF CONTENTS	
PF	OTOCOL SYNOPSIS	3
TA	BLE OF CONTENTS	10
	ST OF ACRONYMS, ABBREVIATIONS AND DEFINITIONS (
	RMS	
	CKGROUND AND RATIONALE	
4.1	XT-150	
4.2		
4.3	1	
4.4		

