5.0 STUDY PURPOSE AND OBJECTIVES

The purpose of this study is to gather evidence for the safety, tolerability, and efficacy of XT-150 as a treatment for pain associated with OA.

- The primary objective of this study is to confirm the safety and tolerability of a single intra-articular dose of XT-150.
- The secondary objective is to establish the analgesic efficacy of a single intraarticular dose of XT-150 as a treatment for pain in participants with OA of the knee.

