6.0 STUDY DESIGN

6.1 Description of the Study

This is a Phase 2 safety, tolerability, and efficacy study of XT-150 in adult participants with pain due to osteoarthritis of the knee. The study will be conducted in 2 Stages, A and B.

Stage A is placebo controlled for six months following intra-articular injection in the Index Knee, which is defined by Kellgren-Lawrence grading and participant-reported pain. The primary efficacy endpoint is 30% response rate in WOMAC pain at Day 180.

Stage B continues for an additional six months of safety and efficacy monitoring during which participants can elect for a second injection to the Index Knee. Active 150 μ g or 450 μ g XT-150 will be randomly chosen for the second injection.

Participants will provide informed consent and meet all study eligibility criteria before any study procedures are initiated. FAST (Appendix 4: Focused Analgesia Selection Test) will be used to select patients who reliably report the magnitude of thermal stimulations.

Baseline confirmation of study eligibility will be completed within one day preceding study drug administration. Study drug will be administered by intra-articular (IA) injection into the joint space of the knee.

About 270 participants will be randomly enrolled into 1 of 3 treatment groups (approximately 90 participants/group). Treatment Groups:

- 1. Placebo (1 mL)
- 2. 150 μg XT-150 (1 mL)
- 3. 450 μg XT-150 (1 mL)

The study will be conducted in 2 stages, A and B:

- A. Placebo controlled for 6 months
- B. Continued follow up for 6 months with the option of randomly receiving a single 150 μg or 450 μg injection as the second injection to the Index Knee (knee dosed in Stage A).

Safety parameters and efficacy endpoints for each participant will be evaluated monthly for about 1 year from the first XT-150 dose (Stage A, Day 0)

The Schedules of Assessments and Procedures are presented in Table 1 and Table 2. Day 0 is defined as the day of study drug administration. Subsequent study days are defined by the number of consecutive calendar days after drug administration.

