6.5 Method of Treatment Assignment and Blinding

After informed consent has been obtained, participants will be screened for study eligibility before enrollment.

In Stage A, participants will be randomly enrolled into one of 3 groups, two XT-150 treatment groups (150 μg or 450 μg) or placebo.

At any time in Stage B up to Day 330, inclusive, participants can elect for a single injection to the knee dosed in Stage A (Index Knee). The second injection dose will be randomized to be either 150 μ g or 450 μ g XT-150. There will be no placebo comparator in Stage B.

Instructions for study drug preparation and dosing are given in Section 8.0.

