13.1 Determination of Sample Size

A total of 270 subjects will be randomized to the 3 treatment groups in a 1:1:1 ratio. The sample size of 90 subjects per group provides more than 90% power to detect a greater responder rate in at least one XT-150 group compared to placebo and 85% power to detect both arms superior to placebo, assuming the responder rate is 30% in each XT-150 group and 10% in the placebo group. As a sensitivity analysis of different assumptions on the response rates in the placebo and XT-150 groups, Table 7 shows the statistical power to detect that at least one treatment group provides greater response than placebo and to detect that both treatment groups provide greater responses.

		Statistical Power (%)				
Placebo response rate (%)	XT-150 response rate (%) in both treatment arms	To detect at least one treatment arm superior to placebo	To detect both treatment arms superior to placebo			
10	25	78	57			
	30	95	85			
	35	99	97			
15	25	38	18			
	30	70	46			
	35	91	77			

Table 7. Treatment Effect That Can Be Detected

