13.4 Safety Analyses

All participants who receive any amount of study drug (Safety Population) will be included in the safety analyses.

Safety will be evaluated by presenting summaries of AEs and vital signs. Safety variables will be tabulated by treatment group.

Adverse events will be graded using the CTCAE v5.0 and will be coded using the Medical Dictionary of Regulatory Affairs (MedDRA®), Version 18 or higher. AEs will be collected for each participant from the signing of the informed consent through the last study visit on Day 360.

A treatment-emergent adverse event (TEAE) is defined as an AE that occurs during or after study drug administration. The incidence of TEAEs will be presented by system organ class (SOC) and preferred term (PT), by SOC, PT, and relationship to the study drug administration, and by SOC, PT, and severity. In addition, the incidence of serious TEAEs and TEAEs leading to discontinuation of study drug will be presented by SOC and PT.

Descriptive statistics for clinical laboratory test results, and vital signs, and for changes from Baseline, will be presented by time point. Baseline is defined as the measurement closest to, but prior to, the administration of study drug. Incidences of potentially clinically significant clinical laboratory results, and vital signs, as defined in the SAP, will also be summarized by time point. A summary of abnormal physical examination findings will also be presented.

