#### 8.2. Safety Data Presentation and Analysis

All clinical safety and tolerability data will be listed for each subject.

Safety data will be summarized using descriptive statistics. Where summaries include changes from baseline, the relevant baseline value will be determined as described in Section 5.5 above.

All adverse events will be listed using MedDRA terms, as coded per the Data Management Plan. The number and percentage of subjects with at least one treatment emergent AE and the number of treatment emergent AEs reported will be summarized by dose level or treatment, grouped according to system organ class and preferred term, using descriptive statistics. The order for system organ class will be according to the Internationally Agreed Order, as per the guidance document MedDRA® *Data Retrieval and Presentation: Points to Consider*, specific to the MedDRA version used for this study. Summaries of TEAEs will also be presented by severity (graded according to the NCI CTCAE version 5.0) and by relationship to investigational product. In these summaries, subjects will be counted at most once per MedDRA term, for the AE of highest severity or least favorable relationship. Summaries will also be presented for SAEs and for AEs leading to study withdrawal.

Clinical laboratory parameters for hematology, serum chemistry, and coagulation will be listed. Summaries of reported results, including changes from baseline and medical

CONFIDENTIAL Page 16 of 27

Protocol No.: XT-150-2-0204 Sponsor: Xalud Therapeutics, Inc.

assessments, will be presented by treatment group and study timepoint. Individual subject profiles will be presented for any laboratory parameters with at least one post-dose value outside the laboratory's reference ranges and deemed clinically significant.

Vital signs will be listed and summarized by dose level / treatment and study timepoint. A summary of changes from pre-dose baseline will also be presented.

Changes in physical examination findings over time will be listed by body system for each subject. It is noted that any untoward findings identified on physical examinations after the administration of the first dose of study medication will be captured as an adverse event if those findings meet the definition of an adverse event as defined in the protocol.

Injection site examinations will be listed and summarized by dose level / treatment and study timepoint.

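### Safety is the primary objective and Stage A has a randomised placebo arm, but the readable safety methods plan per-group summaries only, with no difference from placebo and no measure of precision

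*Protocol*

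**What the plan says.** The synopsis ranks the objectives: "Primary: To confirm the safety and tolerability of intra-articularly-injected XT-150". Efficacy is secondary. Protocol 5.0 repeats the ranking: "The primary objective of this study is to confirm the safety and tolerability of a single intra-articular dose of XT-150".

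The design supplies a concurrent control for six months. Protocol 6.1: "Stage A is placebo controlled for six months following intra-articular injection in the Index Knee". Protocol 13.1: "A total of 270 subjects will be randomized to the 3 treatment groups in a 1:1:1 ratio". The control ends when second injections become available; Protocol 6.5: "There will be no placebo comparator in Stage B".

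The safety methods are per-group summaries throughout:

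- Synopsis, Statistical Methods: "The incidence of treatment-emergent AEs will be presented by treatment group and system organ class and preferred term".
- Protocol 13.4: "Safety variables will be tabulated by treatment group". It lists treatment-emergent events (TEAEs) by class and term, relationship and severity, serious TEAEs, TEAEs leading to discontinuation, and descriptive statistics for laboratory values and vital signs.
- SAP 8.2: "Safety data will be summarized using descriptive statistics". Counts and percentages of participants are given by dose level or treatment, as are injection-site findings. Anti-IL-10 antibody detections are summarised by treatment and time point.

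Contrasts with placebo and two-sided 95% intervals appear in SAP 9.3, for efficacy. Multiplicity control (Protocol 13.5.1, SAP 9.4) and the sample size (Protocol 13.1, SAP 4.5) also concern efficacy only. The post hoc SAP addendum, where readable, is confined to efficacy.

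**The concern.** The trial's first question is about safety, yet the readable plan links no estimate with a stated precision to the answer. Two percentages side by side in groups of 90 do not show how large a difference could lie behind them, and a zero count does not show which rate it rules out.

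Two features of this programme make the placebo contrast worth having. First, Protocol 4.4.2 says that related events have mostly been minor reactions at the injection site, and Protocol 10.8.1 makes such events the events of special interest. A placebo injection can cause these too, so the rate in a dosed group cannot separate drug from procedure; the difference from placebo can. Second, by Protocol Table 3 the only earlier placebo-controlled study had three cohorts with 2 placebo participants each (3 × 2 = 6). The other two studies were open-label without a comparator. This is the first trial in the programme with a control group large enough to support the comparison.

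**Working it through.** **Inputs.** 90 per group, from 270 randomised 1:1:1 (Protocol 13.1); 180 for the two doses together. The documents give no expected adverse event rates, so every event count below is an assumption, shown over a range.

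**The plan's own figure.** No safety power or precision is stated, so there is none to reproduce. The stated efficacy power at 30% v 10% is 95% for at least one dose (Protocol Table 7) and 85% for both. Simulating 400,000 trials with a step-down Dunnett procedure gave 94.8–94.9% and 83.4–83.5% with Fisher exact or continuity-corrected tests, and 96.2% and 87.6% with a logistic Wald test. The group size is therefore consistent with its efficacy purpose.

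**Step 1: no events seen.** The exact upper limit is 1 − α^(1/n).

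| Events | One-sided 95%: 1 − 0.05^(1/n) | Two-sided 95%: 1 − 0.025^(1/n) |
|---|---|---|
| 0/90 | 3.3% | 4.0% |
| 0/180 | 1.7% | 2.0% |

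An event with a true rate of 1% is absent from a group of 90 with probability 0.99^90 = 0.405, about 40%.

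**Step 2: equal observed rates, one dose v placebo.** The Newcombe interval combines the Wilson limits (l, u) of the two groups. When both groups have the same observed rate p and the same size, the half-width is √[(p − l)² + (u − p)²]. For 9/90, p = 0.100, l = 0.0535 and u = 0.1792, so the half-width is √(0.0465² + 0.0792²) = 0.092, or 9.2 points.

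| Observed in each group | Difference | 95% CI (points) |
|---|---|---|
| 0/90 | 0 | ±4.1 |
| 2/90 | 0 | ±5.8 |
| 5/90 | 0 | ±7.5 |
| 9/90 | 0 | ±9.2 |
| 18/90 | 0 | ±11.7 |
| 27/90 | 0 | ±13.2 |

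Groups that look identical are thus compatible with true differences of about 4 to 13 points over observed rates of 0 to 30%.

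**Step 3: what pooling adds and hides.** At 18/180 v 9/90 the interval is −8.7 to +7.0 points, a modest gain over ±9.2. But 9/90 on one dose and 27/90 on the other also pool to 36/180, exactly as 18/90 on each would. Against placebo at 9/90 the single-dose differences are then 0 and +20 points, while the pooled difference is +10. Pooling can support the single-dose results but cannot replace them.

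**Step 4: the time window.** SAP 5.5 attributes an event to Stage A until the Stage B dose. That dose is optional and may come at any time up to Day 330 (SAP 4.4), and events are collected to Day 360 (Protocol 13.4). A participant re-injected at Day 180 contributes about 180 days under this rule; one who never asks for a second injection contributes about 360. If requests differ by group, the groups' percentages rest on unequal follow-up. A like-for-like contrast needs a fixed cut-off.

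**The case against.** Descriptive safety reporting is common in phase 2 and is not an error in itself. The plan contradicts none of its own statements here: it promises no safety precision, and the trial was sized for efficacy. Counts and denominators are planned for every group, so a reader could work out intervals from them. All of this stands, and it limits how strongly the point can be put. It does not supply a stated precision for the primary objective. Nor do percentages built on the SAP 5.5 attribution necessarily yield the right contrast when subtracted.

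Parts of the SAP cannot be read. SAP 4.1 announces a six-month analysis covering efficacy and safety. The contents page lists a Section 11.1 on the unblinded analysis after Stage A, titled for efficacy, but its text is absent, and the table list in Appendix 2 is blank in the public copy. A reader might infer that no planned output anywhere contains a safety contrast. The documents do not support that; only the readable methods text can be said to describe none.

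A reader might also infer that nothing in the plan estimates the drug's risk, or that the objective is to confirm safety against placebo. Neither follows. Per-group incidences are crude estimates of absolute risk and are tabulated with placebo. The objective names no comparator, margin or hypothesis; the comparison comes from the design.

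**Conclusion.** The point holds for the readable text. The primary objective is served by per-group summaries without a planned difference from placebo or a measure of precision, although the design allows both. The size of what goes unstated is about ±9 points at 9/90 in both groups (±4 to ±13 over the range tried), and an upper limit of 3.3% (one-sided) or 4.0% (two-sided) after 0/90. These figures rest on assumed counts, 90 treated participants per group and near-complete follow-up to Day 180.

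It would be tempting to argue that intervals would change the safety conclusion, for instance because a pooled interval excludes zero when the single-dose ones do not. Invented counts can show this only on a knife-edge. Against placebo at 9/90, 18/90 on each dose gives −0.5 to +20.5 points for a single dose and +0.5 to +17.9 pooled. At 17/90 neither interval excludes zero (lower limits −1.5 and −0.5), and at 19/90 both do (+0.4 and +1.6). The case rests on showing precision, not on crossing zero. No data, design feature, sample size or error rate is affected, so this is a cheap improvement.

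**What to change.** Add one table to Protocol 13.4 and SAP 8.2, in the Safety Population.

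- **Outcomes:** any TEAE, related TEAE, serious TEAE, and the injection-site events of Protocol 10.8.1.
- **Window:** onset from Day 0 to the Day 180 visit and before any second injection, in place of the open-ended Stage A attribution in SAP 5.5.
- **Estimates:** risk difference from placebo with 95% CI (Newcombe or Miettinen-Nurminen) for each dose. Show the pooled doses only as a supplement beside the single doses. Where a group has no events, give the exact upper limit and say whether it is one- or two-sided.
- **Interpretation:** treat the intervals as estimates, without hypothesis tests or multiplicity claims, and word the safety conclusion by the rates and differences that they exclude.

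The cost is SAP wording and one more table from data already collected. The safety statement may look slightly less favourable because its uncertainty is shown. If the unreadable Section 11.1 or Appendix 2 already contains such a table, it is enough to cite it in SAP 8.2 and confirm its window.
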